6.1 Inclusion Criteria

- Age 18-60 years old
- Experienced a DSM-5 Criterion A trauma
- Depression Anxiety Stress Scale score (DASS) > 22
- Two or more hyperarousal symptoms
- Normal or corrected to normal vision
- Right-handed
- Fluency in English
- Physically able to travel for study visit attendance
- Stable psychotropic and other medication use for at least 30 days prior to enrollment, and throughout the study period

6.2 EXCLUSION CRITERIA

- Significant chronic disease (e.g. uncontrolled diabetes or cardiovascular disease, advanced liver disease, cancer, etc.)
- Retinal pathology or eye disease like current cataracts or glaucoma, or history of eye surgery
- Currently taking photosensitizing medications
- Currently taking benzodiazepines, selective serotonin re-uptake inhibitors (SSRIs), SNRIs, beta blockers or opioids for their dampening effects on amygdala reactivity
- History of significant light treatment use OR history of light treatment within the past 6 months
- Lifetime psychotic or bipolar disorder
- Current other significant psychological disorder (e.g. OCD)
- Acute suicidal ideation or suicidal behaviors within the last 6 months
- Substance use disorder within last 3 months
- Diagnosed with obstructive sleep apnea, restless leg syndrome, and/or narcolepsy OR at high risk for any of these disorders
- Severe hearing problem
- Intellectual disability or serious cognitive impairment

- History of traumatic brain injury, e.g. any loss of consciousness; any loss of memory for events immediately before or after injury; any alteration in mental status at time of the incident; or focal neurological deficits that may or may not be transient
- Inability to tolerate enclosed spaces (e.g. the MRI machine)
- Ferrous-containing metals within the body
- Pregnant, trying to get pregnant, or breastfeeding
- Current or recent disruptions to normal sleep schedule: e.g. night work or travel outside the Eastern time zone within the past month
- Current psychotherapy
- Epilepsy

6.3 LIFESTYLE CONSIDERATIONS

6.3.1 Alcohol and Drug Use

Participants are asked to refrain from alcohol consumption for 24 hours prior to their study visits. Any participant breathalyzing positive may be:

- Rescheduled to start the study anew if positive test occurs at Visit 2 or 3, prior to start of light treatment
- Withdrawn from the study if positive test occurs at Visits 4-7, after light treatment has started.

Additionally, participants are asked to refrain from taking illicit drugs for the duration of their study enrollment. Any participant testing positive for drug use may be withdrawn from the study as described above.

Test results will remain confidential.

6.3.2 Sleep-wake patterns

Additionally, participants are asked to maintain their usual sleep-wake patterns as documented during the initial week of activity monitoring, and to refrain from napping in the 4 hours immediately after light therapy. Participants might be asked to wake up an hour earlier than usual to accommodate the light treatment in context of their life schedule (e.g. work or childcare obligations).

6.3.3 Medication and Concomitant therapies

Participants are asked to maintain their current (from time of enrollment) treatments including all medications and non-pharmacological strategies throughout their participation in the study.

6.3.4 Naps

Participants are asked not nap within 4 hours of completing their treatment.

6.4 Strategies for Recruitment & Retention

We will use a multi-pronged recruitment approach to target both community members and clinical populations with traumatic stress living in Southeastern Michigan.

6.4.1 Online Recruitment

Our online recruitment strategies will include craigslist.com, Facebook, and umhealthresearch.org, the University of Michigan Research Registry. We will work with MICHR's Recruitment Core to design targeted ads to specific geographical areas (including, but not limited to the surrounding Ann Arbor/Ypsilanti and greater Detroit regions), age groups, and multiple races and ethnicities.

6.4.2 [name]

[name] has an ongoing non-treatment study for individuals with PTSD. Individuals who do not meet the diagnostic criteria for PTSD yet still report traumatic stress and those individuals who have completed the study will be offered the opportunity to participant in the current protocol and/or speak with the study team.

6.4.3 Flyers

We will distribute flyers to local clinics and local support groups, including but not limited to those in the surrounding Ann Arbor/Ypsilanti and greater Detroit regions. We will also distribute flyers to the Ann Arbor VA (where [name] has a Without Compensation [WOC] appointment). We will post fliers on the Wayne State University campus.

6.4.4 Data Direct/EMERSE

We will use two of the online self-serve tools provided by the University of Michigan Data Office for Clinical and Translational Research to access clinical data as a means of identifying potential participants with a history of trauma or PTSD. Once identified, these individuals will be approached initially via an introductory letter, email, or text inviting them to contact the study team for information.

6.4.5 Possible future strategies

If our initial strategies fail to generate sufficient enrollment numbers to achieve our accrual goals, we will consider alternatives, with no specific plan as of yet. We will submit an amendment before embarking on any additional strategies.

6.4.6 Pre-screening

Prospective participants will participate in a series of pre-screening surveys: first they complete an online survey to determine basic eligibility followed by a telephone interview during screening questions for trauma history, psychiatric disorders, and other potentially sensitive criteria are discussed. Once deemed eligible at this stage, individuals are scheduled for an in-person screening visit at which additional screening procedures will occur. In advance of this visit they are sent an example study protocol (i.e. schedule) and a pre-study sleep log.

6.4.7 Retention

We use a number of approaches to promote retention of participants throughout the study:

- Schedule all study visits on Day 1
- Daily outgoing communication (e.g. text, phone call, etc.) to support intervention adherence
- Weekly visits to review Re-Timer use and daily logs with participants
- Provide monetary incentive and travel stipend per visit plus a bonus for completing the entire study.

 Offer free cab rides to participants with no access to timely public transportation or a car/rides with friends and family.

During weekly lab meetings, the team will review overall participant statuses, as well as enrollment numbers and recruitment sources, and the number of withdrawals and lost-to-follow ups to allow for adjustments in the recruitment strategy as needed.

In aggregate, these strategies have proven successful in our other studies of morning light treatment. If, despite our efforts, enrollment is lacking, we will work with Co-I [name] who has a relationship with Wayne State University Stress, Trauma & Anxiety Research Clinic to expand our reach into the Detroit area. And, we will work with the Michigan Community Outreach Program and the NIMH Outreach Partnership Program to help disseminate educational and study information to the public as a means of promoting research participation.

6.5 Participant Incentives

Participants are eligible for up to \$1210.00 in incentive payments. The payment plan was designed to partially compensate individuals for the burden of the study visits and associated travel costs, as well as promote study completion by including a bonus for finishing the protocol. Participants will be paid as the study progresses for those parts of the study completed.

- Visit 1 \$20 for screening visit eligibility confirmation and consent
- Visit 2 Receive study materials, no incentive
- Visit 3 \$225
 - \$75 for completing the baseline week of actigraphy and activity/sleep logs
 - \$150 for completing the clinical assessments and fMRI
- Visit 4 \$75 for completing previous week of actigraphy and activity/sleep logs
- Visit 5 \$175
 - \$75 for completing previous week of actigraphy and activity/sleep logs
 - \$100 for completing clinical assessments
- Visit 6 \$75 for completing previous week of actigraphy and activity/sleep logs
- Visit 7 \$400
 - \$75 for completing previous week of actigraphy and activity/sleep logs
 - \$150 for completing clinical assessments and fMRI
 - \$175 bonus for completing the study
- Travel stipend \$80 \$240 for Visit 1-7 (e.g. up to 8 visits to the research clinic including coming to the clinic twice for activities associated with Visit 2)
 - The travel stipend will be \$10 \$30 per study visit to account for the varying distance which different participants must travel to the lab. The travel stipend will always be at least \$10, increasing by approximately \$1 per mile traveled, up to a maximum of \$30 for 30 miles or more. Mileage will be rounded up to the nearest whole number to determine the dollar amount given, e.g., 10.4 miles would amount to a travel allowance of \$11.
 - Participants will be asked to verify from which location they will be traveling to lab visits during their phone screen and reconfirm this at Lab Visit 1, which will determine their stipend for Visits 1-7.

o If the fMRI occurs on a different day from the research clinic visit, the travel stipend is only provided for the visit to the clinic (e.g. Rachel Upjohn Building).

6.6 SCREEN FAILURES

Criteria for screen failures include:

- Positive urine drug screen at baseline
- Study team learns of study exclusion criteria that arises during the baseline week

7 STUDY INTERVENTION

7.1 DESCRIPTION

Morning light treatment is a non-invasive and low-risk therapeutic option for trauma-related stress and disturbed mood and arousal. The light is transmitted directly from retinal photoreceptors to the amygdala, a key brain region in the manifestation of traumatic stress symptoms. The light is delivered using a pair of Re-Timer glasses that have been adjusted for each participant to optimize the light delivery.

7.2 Administration & Dosing

- Self-administered in own home
- First thing upon waking (or up to 1 hour earlier to accommodate morning commitments like work or childcare)
- Light intensity is about 500 lux
- Duration is pre-set for either 15, 30 or 60 minutes/day depending on study arm
- Daily administration for 4 consecutive weeks (starting the morning after Visit 3)

7.3 FIDELITY

- Participants are provided with a pre-set alarm clock to the prescribed wake up time (based on the baseline week of actigraphy); they are instructed to use their own alarm clock as a backup.
- The Re-Timer glasses are configured with a pre-set timer based on prescribed duration. Participants are to activate the timer at the start of each treatment session.
- Participants will record times of use and any interruptions or alterations to the treatment session in the daily sleep/activities log.
- Participants will receive a daily communication asking a Yes/No question completion of light therapy.
- Participants will meet with the study team weekly to review light treatment data (downloaded from the Re-Timer glasses).

7.4 Measures to Minimize Bias

7.4.1 Randomization

Participants will be randomized at Visit 3, after the week-long baseline period, to one of 3 daily light durations (15, 30 or 60 minutes/day) using a secure web-based treatment assignment system implemented by CSCAR (cascar-randomization.appspot.com). This system uses a minimization approach to reduce imbalances in covariates following each round of treatment assignment by using non-uniform assignment probabilities for the different treatment groups. The following minimization variables will be used: combat vs. non-combat index trauma; DASS; use of psychoactive medication; ages, sex and race.

7.4.2 Blinding

The outcomes assessor will be blinded to study arm, along with rest of the study team *except for* the PI, study coordinator and designated research assistants. These individuals need to remain unblinded to perform safety assessments and provide feedback on intervention compliance. Blinded staff will wear buttons as an upfront visual cue to remind participants not to talk about their treatment.

7.5 CONCOMITANT THERAPY

Patients are allowed to continue their usual care throughout the study. All concomitant treatments must be stable for at least 30 days prior to enrollment, *and* be maintained throughout the study period. **Allowable therapies** include, but are **not limited to**:

 Prescribed psychotropic medications (except for benzodiazepines, SSRIs, SNRIs, beta blockers, and opioids)

7.6 CONTRAINDICATED THERAPY

Current participation in psychotherapy or other non-pharmacological treatments for trauma stress is an exclusion criterion because of potentially confounding effects on study outcomes.

Likewise, current or new use of benzodiazepines, SSRIs, SNRIs, beta blockers, or opioids is contraindicated because of their potential effects on amygdala reactivity.

8 END-OF-INTERVENTION/END-OF-STUDY

8.1 DISCONTINUATION OF INTERVENTION

Use of the Re-Timer will be stopped in the event of:

- Significant clinical deterioration or expressed suicidal ideation at the determination of the study team
- Severe treatment side effects at the determination of the study team
- Significant decline in physical health making compliance with the intervention either ill-advised or challenging to complete
- Participant request to discontinue therapy

Reasons for discontinuation will be documented, and all outcome assessments will proceed as scheduled, if possible.

8.2 Participant Discontinuation or Withdrawal from Study

Reasons why a participant might be withdrawn from the study:

- Participant request
- Any new diagnosis that would be considered part of the original exclusion criteria for this study
- Positive breathalyzer or drug test at the study at Visits 3, 4, 5 or 6
- Start of new treatment or therapy during study period
- Significant study intervention non-compliance, i.e. inability or unwillingness to complete study intervention or outcome assessments
- Any clinical event or other medical condition or situation such that continued participation in the study would not be in the best interest of the subject
- If the participant meets an exclusion criterion (either newly developed or not previously recognized) any time
- Lost-to-follow up

If possible, reasons for withdrawal will be documented. Data from dropouts or withdraws will be retained to minimize data loss.

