9.7 FMRI

Amygdala reactivity will be measured using fMRI and change in BOLD signal measures across the study period. Images will be acquired using an Echo-Planar Imaging sequence (TR=800 ms, FOV=23, slice=2.4mm, 96x96 matrix) to measure brain function at rest and during the EFAT task, optimized to reduce susceptibility artifact. fMRIs (initially at visits 3, 5 and 7 but later changed to only visits 3 and 7) will be scheduled at the North Campus facility and must occur within 7 days of the clinician-administered and self-reported assessments of trauma stress and mood (see Section 9.3)

9.7.1 fMRI Practice

As part of the screening process, individuals will be able to lie in the mock scanner located at the Rachel Upjohn Building. This scanner is built to size, and includes simulating scanner noise from speakers so people can hear the noises associated with scanning.

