11 STATISTICAL CONSIDERATIONS

11.1 GENERAL APPROACH

The objective of this study is to establish a signification dose response relationship between the duration of morning light treatment and reduction in amygdala reactivity from baseline to treatment week 2 (study week 3) and/or treatment week 4 (study week 5).

Statistical analyses will include intent-to-treat and completer analysis. Data will be analyzed using responses at all three times (baseline, 2 [when data available] and 4 weeks) as dependent variables using a mixed-effects longitudinal model [106, 107] with participants as random intercepts to account for between participant variability and time as a predictor.

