11.1.2 Go/No-go Criteria

A meaningful reduction in amygdala reactivity (Cohen's d≥0.5) must be observed with one of the three daily light durations at treatment week 2 and/or treatment week 4.

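### Section 8.2 permits withdrawal from the study when new treatment starts and does not say assessments continue; under the two-scan schedule that can remove a participant's only post-baseline amygdala value

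*Combined protocol and SAP*

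**What the plan says.** Section 8.2 introduces its list as "Reasons why a participant might be withdrawn from the study". Two entries matter here: "Start of new treatment or therapy during study period" and "If the participant meets an exclusion criterion (either newly developed or not previously recognized) any time". New psychotherapy or a new SSRI would fall under both, because each is an exclusion in 6.2. For withdrawn participants, 8.2 says that the data already held are kept. It describes no later assessment and no exit scan.

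Section 8.1 covers stopping the light alone. There, "all outcome assessments will proceed as scheduled, if possible".

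Section 9.7 gives the scan schedule as "initially at visits 3, 5 and 7 but later changed to only visits 3 and 7", and the schedule of activities in 1.3 agrees. Visit 7 is therefore the only scheduled post-baseline scan. Participants enrolled while Visit 5 was still scanned may also have a week 2 value; their number is not given.

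On analysis, 11.1 states: "Statistical analyses will include intent-to-treat and completer analysis". The mixed model takes responses at "baseline, 2 [when data available] and 4 weeks". Under 11.1.2, a reduction of Cohen's d≥0.5 "must be observed with one of the three daily light durations at treatment week 2 and/or treatment week 4". Section 11.2 names pattern-mixture, selection or other models if non-ignorable missingness is detected.

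**The concern.** The two sections handle similar clinical courses differently. Someone who deteriorates and stops the light stays under assessment by 8.1. Someone who deteriorates, is referred to care (which 9.10.1 and 12.3.1 allow) and then starts treatment may be withdrawn under 8.2. No rule says which path applies. With one post-baseline scan, the choice decides whether that person contributes anything on change in amygdala reactivity.

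Two results depend on that scan. An intent-to-treat analysis would then rest on assumptions for the missing value. The go/no-go rule needs only one arm of about 22 to reach d≥0.5, and the plan does not say whether participants who start new treatment count in that d.

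The protocol has a sound reason to worry about new treatment: 6.2 and 7.6 say that the contraindicated drugs dampen or may affect amygdala reactivity. That reason bears on how a scan is analysed. It does not settle whether the scan should be taken.

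**Working it through.** **Structural check**

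1. Ground: starting new treatment is a permitted reason for withdrawal from the study (8.2).
2. Follow-up: continued assessment is stated for stopping the light (8.1) and not stated for withdrawal (8.2). That no scan follows is inferred from this silence; 8.2 does not forbid one.
3. Scans: Visits 3 and 7 only (9.7, 1.3). Withdrawal between them leaves a baseline value and no change value.
4. Model: baseline is one of the dependent variables (11.1), so the participant still contributes a baseline value but nothing on change.
5. Missing-data models (11.2): these can examine the effect of the loss but cannot supply the scan.

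**Scale**

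Enrolment is 66 in three arms (sections 6 and 5.1). The plan gives no alpha, power, SD or dropout rate, so 66 cannot be reproduced. With equal arms (an assumption), 66/3 = 22. One lost scan is 1/22 = 4.5% of an arm; two are 2/22 = 9.1%.

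**Illustration only**

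The number of starters, their difference from the rest of the arm and the true d are all assumed; none is in the documents.

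Shift in an arm's mean change, starters included versus excluded = (k/22) × difference:

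| Starters k | Difference | Shift | Share of the 0.5 threshold |
|---|---|---|---|
| 1 | 0.5 SD | 0.023 SD | 5% |
| 1 | 1.0 SD | 0.045 SD | 9% |
| 2 | 0.5 SD | 0.045 SD | 9% |
| 2 | 1.0 SD | 0.091 SD | 18% |

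Chance that one arm shows d≥0.5. Here d = mean change / SD of change (the plan does not define it) and the true d in non-starters is 0.3. With n observed and no starters among them, P = P(T ≥ 0.5√n), where T is noncentral t with n−1 degrees of freedom and noncentrality 0.3√n. This gives 0.196 for n=22, 0.202 for n=21 and 0.208 for n=20. The included cases are simulated.

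| Starters in the arm | Excluded | Included, reduction 0.5–1.0 SD smaller | Included, reduction 0.5–1.0 SD larger |
|---|---|---|---|
| 1 of 22 | 0.20 | 0.17–0.14 | 0.22–0.24 |
| 2 of 22 | 0.21 | 0.14–0.09 | 0.25–0.29 |

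The rule passes on any one of three arms. Take true d = 0.3 in all arms, two starters in one arm and none in the others. Then P(go) = 1 − (1 − p)(1 − 0.196)², where p is the chance for the arm with starters and (1 − 0.196)² = 0.646:

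- excluded: 1 − 0.792 × 0.646 = 0.49
- included, reduction 1.0 SD smaller: 1 − 0.911 × 0.646 = 0.41
- included, reduction 1.0 SD larger: 1 − 0.707 × 0.646 = 0.54

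At the level of the actual decision the swing is modest, and it can go either way.

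**The case against.** The strongest reply is that this is a defensible choice in a mechanistic trial. Stable treatment is a condition of participation (6.1, 6.3.3, 7.5), the endpoint is amygdala BOLD signal, and a scan taken on a new SSRI no longer isolates the effect of light. Letting such a scan count towards go is a choice of estimand, not the repair of an error. This stands. It is why the plan must say which result governs, and why inclusion alone is not the remedy. It does not justify leaving the scan untaken: a collected scan can be analysed both ways.

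A second reply is that 8.2 only permits withdrawal, that 8.1 may still apply to someone who deteriorates, and that section 10 defers to a Data and Safety Monitoring Plan not included here, which may deal with follow-up. This also stands, and it limits the point to a missing statement in 8.2. Discretion has its own cost, though: withdrawal decisions rest with the investigators (9.10.1, 12.3.1), and 7.4.2 leaves the principal investigator unblinded.

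Third, 11.1 and 11.2 already plan a completer analysis and missing-data models. They describe the effect of the loss but do not replace the value.

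Finally, other grounds in 8.2, such as non-compliance or a positive drug test, lose the same scan. That is so; they are outside this point.

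**Conclusion.** The point holds in a limited form. Using the new-treatment ground in 8.2 before Visit 7, under the two-scan schedule and with no further scan, leaves no post-baseline amygdala value for the planned intent-to-treat analysis or for d. Each case costs about 4.5% of an arm's Visit 7 scans if arms are equal.

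A reader might infer that the protocol requires withdrawal of anyone who starts treatment, or forces a choice between care and staying in the study. The documents do not support that: 8.2 is permissive, and 9.10.1 and 12.3.1 allow referral without withdrawal. A reader might also infer that the go/no-go result is biased in a known direction. The documents give no number of starters, no effect of new treatment on their scans and no difference between arms, so neither size nor direction can be estimated. The probabilities in the working are assumed illustrations.

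This is a worthwhile low-cost improvement, held with medium confidence.

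**What to change.** **In 8.2:** state that starting new treatment, including psychotherapy or a contraindicated drug, is not in itself a reason to end follow-up. The light may be stopped under 8.1. Scheduled assessments and the Visit 7 scan continue if safe and the participant agrees. Record the date and type of the new treatment.

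**In 11.1.2 and 11.2:** report the dose-response test and each arm's d twice, once with all available scans (intent-to-treat) and once with scans after the start of new treatment excluded. State in advance which result governs go/no-go, and do not let a go rest only on scans acquired on new treatment.

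**Cost:** wording in three sections, with no added visits or scans. The daily log already captures medication use (1.3, footnote 2); new psychotherapy needs one added question.

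**Downside:** some Visit 7 scans will be drug-affected and could overstate the reduction. For participants with no week 2 scan, the exclusion analysis drops their only post-baseline value, so for them it matches what withdrawal gives now. The gain is that the all-scans result can be shown beside it.
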